12.2. Assessment of Safety

- 1. The Columbia Suicide Severity Rating Scale (C-SSRS) (Posner, Brown et al. 2011) will be administered by trained research personnel at each session to thoroughly assess suicide risk. If a participant reports experiencing either suicidal ideation or suicidal behavior, research personnel will collect more information from the participant to deliver to either [name]. Clinical personnel will decide if an acute assessment is required. Acute assessment may include facilitating contact of the participant with their psychiatrist or primary care physician to establish a plan for safety, continued care, and follow-up. If the participant does not have an established provider, [name] will assist in establishing a care plan. If at any point during the assessment, the participant is deemed an imminent risk of harm to self or others, study personnel will enlist the aid of campus security to ensure that the participant is safely escorted to the Emergency Department for further care. [name] will decide if participation should be stopped after the acute assessment. If an acute assessment is required, then participation will be halted.
- 2. A stimulation side effects questionnaire will be administered at the end of each stimulation session. This tool will be used as a safety measure and to collect data on the participant's experience. A similar questionnaire was used in a previous study (IRB# 13-2995) to determine ability to successfully blind the participants using sham transcranial current stimulation.
- 3. We screen and exclude individuals with any medical or neurological illness for which symptom presentation or treatment could interfere with study participation. We further emphasize that there has never been a single report of a

seizure that resulted from transcranial alternating current stimulation (Matsumoto & Ugawa, 2016), and existing guidelines suggest that both tACS and tDCS are safe (Antal et al., 2017).

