Participation Duration	Study participation for each participant will be approximately 4 weeks. Completion includes three in-person sessions: a baseline clinical assessment and EEG session, an intervention session, and a follow-up assessment and EEG session two weeks later. The baseline clinical assessment and EEG session will take approximately 3 hours. The intervention session will take approximately 2 hours. The follow-up visit will take approximately 2.5 hours. Participants will be sent questionnaires to complete online 4 weeks after the intervention visit. These questionnaires are expected to take approximately 0.5 hours to complete. We estimate that total participation will take approximately 8 hours.
Enrollment Duration	8 months

2. Introduction

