5.7. Blinding

This study is designed to be double-blind. This means that the participant and the researchers are unaware of each participant's assignment until the completion of all data collection. This is accomplished using the randomization codes described above. Furthermore, this study utilizes an active sham stimulation. This means that the active sham condition includes some stimulation, mimicking the skin sensations associated with tACS. In our previously concluded trial, participants in the delta-beta tACS and active sham groups responded similarly to the blinding questionnaire, indicating that our active sham stimulation successfully blinded the participants.

6. Treatment Design: Procedures

Description All participants will receive the behavioral activation (BA) psychotherapy intervention. This intervention occurs in a single 90-minute session. Participants are randomized to receive either an active stimulation or sham stimulation using transcranial alternating current stimulation (tACS).

Acquisition The DC-STIMULATOR MC is a CE-certified medical device is owned and operated by the Carolina Center for Neurostimulation / [name] lab.

Concomitant Therapies Participants will be ineligible to participate in this study if they are currently receiving another form of psychotherapy, TMS, and/or ECT. Individuals prescribed psychiatric medication must be on a stable dose (>4 weeks). Concomitant medications will be logged at the first session. Participants will be requested to include the dosing for these therapies (i.e., how often per day, how much in each pill, how many pills) as well as when they were first prescribed the medication.

7. Schedule of Activities and Procedures

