All AEs including local and systemic reactions not meeting the criteria for SAEs will be captured on the appropriate case report form (CRF). Information to be collected includes event description, time of onset, clinician's assessment of severity, relationship to study product (assessed only by those with the training and authority to make a diagnosis), and time of resolution/stabilization of the event. All AEs occurring while on study must be documented appropriately regardless of relationship. All AEs will be followed to adequate resolution. Any medical condition that is present at the time that the participant is screened will be considered as baseline and not reported as an AE. However, if the study participant's condition deteriorates at any time during the study, it will be recorded as an AE. Changes in the severity of an AE will be documented to allow an assessment of the duration of the event at each level of severity to be performed. AEs characterized as intermittent require documentation of onset and duration of each episode.

Research personnel will record all reportable events with start dates occurring any time after informed consent is obtained until 7 (for non-serious AEs) or 30 days (for SAEs) after the last day of study participation. At each study visit, research personnel will inquire about the occurrence of AE/SAEs since the last visit. Events will be followed for outcome information until resolution or stabilization. All AEs including local and systemic reactions not meeting the criteria for SAEs will be captured on the appropriate case report form (CRF). Information to be collected includes event description, time of onset, clinician's

assessment of severity, relationship to study product (assessed only by those with the training and authority to make a diagnosis), and time of resolution/stabilization of the event. All AEs occurring while on study must be documented appropriately regardless of relationship. All AEs will be followed to adequate resolution.

Any medical condition that is present at the time that the participant is screened will be considered as baseline and not reported as an AE. However, if the study participant's condition deteriorates at any time during the study, it will be recorded as an AE.

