13.7. Clinical Monitoring Plan (CMP)

The purpose of the monitoring plan is to present the approach of the Carolina Center for Neurostimulation to monitoring clinical trials. The plan facilitates compliance with good clinical practice.

- (a) The rights and well-being of human participants are protected.
- (b) The reported trial data are accurate, complete, and verifiable from source documents.
- (c) The conduct of the trial is in compliance with the currently approved protocol/amendment(s), with GCP, and with applicable regulatory requirement(s).

This section identifies key monitoring activities and specifies the data to be reviewed over the course of a clinical trial. This is a single site, investigator initiated, clinical trial so there will be no site monitoring plan in place.

The latest version of the approved IRB application for this clinical trial will be followed at all times. This responsibility falls in the hands of the trained research personnel. If at any time there is a deviation from protocol, the deviation from protocol log will be filled out. All team members will be trained on how and when to use this log. Deviations will be sent to IRB every 4-6 weeks (if necessary).

Data will be verified for completeness following every study session and all data will be entered into REDCap, a secure online database. After a participant has completed their participation (full completion through the 2-week follow-up visit or because they withdrew prior to completion), data will be rereviewed for completeness and accuracy. After all data has been collected, data will be re-reviewed by another lab member who was not involved with the data collection process.

AE and SAE are clearly defined in the Master Protocol. Documents of AE and SAE can be found in the study binder on file within [name]. It is responsibility of trained research personnel to report all events to the PI. Reporting of AEs and SAEs is described within Section 12.3.

The PI and Co-I will have read-only access to the REDCap database. This allows the PI and Co-I to view reports that provide information on any missing data on an individual participant basis, but does not allow them to add, change or input any data.

Quality Assurance and Quality Control

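### The suicide-risk rule in 12.2 halts participation as a whole, so a stop after stimulation that is not lifted spares no exposure and loses the 2-week HDRS

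*Combined protocol and SAP*

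**What the plan says.** Section 12.2 states that the C-SSRS "will be administered by trained research personnel at each session to thoroughly assess suicide risk". Any reported ideation or behaviour is passed to clinical personnel, who judge whether an acute assessment is needed. A clinician "will decide if participation should be stopped after the acute assessment", and the next sentence reads: "If an acute assessment is required, then participation will be halted". Section 12.4 repeats both sentences.

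Elsewhere, participation covers follow-up as well as treatment. The synopsis says "Study participation for each participant will be approximately 4 weeks", and Section 13.7 describes the end of participation as "full completion through the 2-week follow-up visit or because they withdrew prior to completion". Treatment is a single occasion: in Section 6, "This intervention occurs in a single 90-minute session", with stimulation in the final 30 minutes (Section 7.6).

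The HDRS is taken at baseline and at Visit 2 only (Table 2). The C-SSRS is scheduled at Visits 0, 1 and 2 (Table 3 and Section 7.2). The week-4 contact is online self-report and includes neither.

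Under Section 12.3, new events are recorded "until 7 (for non-serious AEs) or 30 days (for SAEs) after the last day of study participation".

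**The concern.** In a trial with one treatment session, stopping the intervention and stopping follow-up have different consequences, and the rule uses one word for both. Before treatment, a stop protects the participant from exposure. After stimulation there is no exposure left to withhold. A stop that is not lifted then only ends observation of someone just identified as being at possible risk.

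Two things are at stake. First, the primary outcome goes missing because of suicidality, which is related to depression severity, so the missing value may be informative. A pre/post ANOVA has no change score for that person. Second, the last scheduled C-SSRS is not done, and the window for recording new adverse events closes earlier.

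The pathway is open to eligible participants. Exclusion requires C-SSRS items 4 or 5, whereas the process in 12.2 starts at any reported ideation or behaviour, so people enrolled with lesser ideation can enter it.

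**Working it through.** **Step 1. Trace the rule through the schedule, assuming that participation is not resumed.**

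| When triggered | Exposure spared | What is lost |
|---|---|---|
| Visit 0 | All | Nothing of concern; this is a screening exclusion |
| Visit 1, before BA | BA and stimulation | 2-week HDRS and C-SSRS, but exposure is spared |
| Visit 1, after stimulation | None | 2-week HDRS, SHAPS-C, EEG task, last scheduled C-SSRS |
| Between Visits 1 and 2 | None | The same, if the rule is applied to unscheduled reports |
| Visit 2 | None | Little: whatever is not yet done that day, and the week-4 questionnaires |

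The problem lies in the third and fourth rows. The third is possible because Section 7.2 places the C-SSRS at the intervention visit without saying whether it comes before or after stimulation. The fourth is less certain: Section 12.3 lets participants report events outside visits, but nothing there attaches the halt rule to such a report.

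**Step 2. Does any text keep a stopped participant in follow-up?** None does. The sentence in Section 7.6 ending data collection is written for people who elect to withdraw, so it neither requires nor prevents a Visit 2 for someone stopped by a clinician. The list of reasons for discontinuing the intervention in 7.6 has no follow-up provision attached.

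**Step 3. Recording window for new events.** Take Visit 1 as day 0 and a stop on day s. Recording ends on day s + 7 (non-serious AEs) or s + 30 (SAEs).

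- Stop on day 0: days 7 and 30.
- Completer, participation ending at Visit 2 (day 14): days 21 and 44.
- Completer, participation ending at week 4 (day 28): days 35 and 58.

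The shortfall is 14 − s or 28 − s days, the same for AEs and SAEs. For a stop on day 0 it is 14 or 28 days. For a stop on day 13 it is 14 − 13 = 1 or 28 − 13 = 15 days. The range is therefore about 1 to 28 days.

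**Step 4. Effect of one lost HDRS on Aim 1.** With 20 per arm, one participant is 1/20 = 5% of an arm. In units of the SD of HDRS change, the standard error of the between-arm difference is √(2/20) = 0.316. The documents do not say how far such a participant would lie from the rest of the arm; I assume 0.5 to 1.5 SD. Leaving that person out moves the arm mean by:

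- 0.5/20 = 0.025 SD, and 0.025/0.316 = 8% of the standard error;
- 1.5/20 = 0.075 SD, and 0.075/0.316 = 24% of the standard error.

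The documents give no trigger rate, so neither the number of stops nor the net direction of bias can be derived.

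**The case against.** The strongest reply is that the rule already provides for judgement. If halting were permanent, the clinician would have nothing left to decide, so the coherent reading is a pause followed by a clinical decision, and no sentence bars Visit 2. This stands to the extent that nothing need be lost if the halt is lifted. It does not settle the matter. The screening text in Sections 5.3.2 and 7.1 pairs acute assessment with stopping or terminating participation, and 12.2 sets no default for follow-up when the clinician does stop someone.

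It is also fair that the window is narrow, that care continues, and that for recorded events "Events will be followed for outcome information until resolution or stabilization". That follow-up does not supply an HDRS or a C-SSRS. Section 8.1 requires reasons for drop-out to be documented and gives alternative missing-data methods a role in sensitivity analyses. It names no method, but that is a general gap and not a fault of this rule.

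A reader might infer three stronger points that the documents do not support:

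- **Sections 5.6 and 7.7 conflict on replacement.** They can be read together. Table 3 puts randomization at Visit 0, and 7.7 bars replacement only for randomized participants who received all or part of the intervention. The 10 spare codes can serve people who leave before Visit 1. For a stop after stimulation, 7.7 is clear: no replacement.
- **The C-SSRS is given only once.** Section 12.4 mentions only the first session, but 12.2, 7.2 and Table 3 agree on Visits 0, 1 and 2. This is an editorial slip.
- **Every early stop shortens event recording by at least 14 days.** That holds only for a stop on day 0.

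**Conclusion.** The point holds conditionally. It requires a trigger after stimulation and before Visit 2, and a clinician who does not resume participation. Under both conditions the stop spares no exposure and loses the only post-treatment HDRS and the last of three scheduled C-SSRS assessments. It also closes the recording of new events about 1 to 28 days sooner.

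The effect on Aim 1 is modest: 5% of an arm per participant and, on the assumed 0.5 to 1.5 SD deviation, 8% to 24% of one standard error. The number affected is unknown and probably small. The text does not show that the rule ends follow-up for everyone who needs an acute assessment; it leaves that possible where it need not be. The change is worth making because it is safer, less prone to bias, and cheap.

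**What to change.** 1. In Section 7.2, state that the Visit 1 C-SSRS is given before BA and stimulation, and that the intervention is withheld if items 4 or 5 are positive. This agrees with the rule in 7.6 on newly met exclusion criteria.
2. In Sections 12.2 and 12.4, replace the last two sentences of the C-SSRS item. Say that study procedures pause during an acute assessment and that the clinician then decides whether any remaining intervention is given. Say also that the 2-week HDRS and C-SSRS are still sought unless the participant withdraws consent or the clinician judges the visit unsafe. State that these participants are analysed in their assigned arm.
3. As an editorial correction, align the C-SSRS timing in 12.4 with 12.2.

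The cost is an IRB wording amendment and some effort to follow up at-risk participants, bounded by clinician discretion. No visit or measure is added, and the sample size does not change.

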12.3. Unanticipated Problems, Adverse Events, Serious Adverse Events

Unanticipated Problems: The Office for Human Research Protections (OHRP) considers unanticipated problems involving risks to participants or others to include, in general, any incident, experience, or outcome that meets all of the following criteria:

- Unexpected in terms of nature, severity, or frequency given (a) the research procedures that are described in the protocol-related documents, such as the Institutional Review Board (IRB)- approved research protocol and informed consent document; and (b) the characteristics of the participant population being studied;
- Related or possibly related to participation in the research ("possibly related" means there is a reasonable possibility that the incident, experience, or outcome may have been caused by the procedures involved in the research); and
- Suggests that the research places participants or others at a greater risk of harm (including physical, psychological, economic, or social harm) than was previously known or recognized.

Adverse Event (AE) Definitions: Adverse event means any untoward medical occurrence associated with the use of an intervention in humans, whether considered intervention-related (21 CFR 312.32 (a)).

Serious Adverse Events (SAE) Definition: An adverse event (AE) or suspected adverse reaction is considered "serious" if, in the view of the investigator, it results in any of the following outcomes: death, a life-threatening adverse event, inpatient hospitalization or prolongation of existing hospitalization, a persistent or significant incapacity or substantial disruption of the ability to conduct normal life functions, or a congenital anomaly/birth defect. Important medical events that may not result in death, be life-threatening, or require hospitalization may be considered serious when, based upon appropriate medical judgment, they may jeopardize the participant and may require medical or surgical intervention to prevent one of the outcomes listed in this definition. Examples of such medical events include allergic bronchospasm requiring intensive treatment in an emergency room or at home, blood dyscrasias or convulsions that do not result in inpatient hospitalization, or the development of drug dependency or drug abuse.

Grading the Severity of Adverse Events and Events of 'Special Interest':

All adverse events (AEs) will be assessed by the principal investigator and/or co-investigator(s) using the following guidelines:

- Mild Events require minimal or no treatment and do not interfere with the participant's daily activities.
- Moderate Events result in a low level of inconvenience or concern with the therapeutic measures. Moderate events may cause some interference with functioning.
- Severe Events interrupt a participant's usual daily activity and may require systemic drug therapy or other treatment. Severe events are usually potentially life-threatening or incapacitating. Of note, the term "severe" does not necessarily equate to "serious".

Relatedness Definition:

All adverse events (AEs) must have their relationship to study intervention assessed by the principal investigator and co-investigator(s) who examines and evaluates the participant based on temporal relationship and their clinical judgment. The degree of certainty about causality will be graded using the categories below. In a clinical trial, the study product must always be suspect.

• Definitely Related – There is clear evidence to suggest a causal relationship, and other possible contributing factors can be ruled out. The clinical event, including an abnormal laboratory test result, occurs in a plausible time relationship to study intervention administration and cannot be

Protocol Number <#>

explained by concurrent disease or other drugs or chemicals. The response to withdrawal of the study intervention (dechallenge) should be clinically plausible. The event must be pharmacologically or phenomenologically definitive, with use of a satisfactory rechallenge procedure if necessary.

- Probably Related There is evidence to suggest a causal relationship, and the influence of other factors is unlikely. The clinical event, including an abnormal laboratory test result, occurs within a reasonable time after administration of the study intervention, is unlikely to be attributed to concurrent disease or other drugs or chemicals, and follows a clinically reasonable response on withdrawal (dechallenge). Rechallenge information is not required to fulfill this definition.
- Potentially Related There is some evidence to suggest a causal relationship (e.g., the event occurred within a reasonable time after administration of the trial medication). However, other factors may have contributed to the event (e.g., the participant's clinical condition, other concomitant events). Although an AE may rate only as "possibly related" soon after discovery, it can be flagged as requiring more information and later be upgraded to "probably related" or "definitely related", as appropriate.
- Unlikely to be related A clinical event, including an abnormal laboratory test result, whose temporal relationship to study intervention administration makes a causal relationship improbable (e.g., the event did not occur within a reasonable time after administration of the study intervention) and in which other drugs or chemicals or underlying disease provides plausible explanations (e.g., the participant's clinical condition, other concomitant treatments).
- Not Related The AE is completely independent of study intervention administration, and/or evidence exists that the event is definitely related to another etiology. There must be an alternative, definitive etiology documented by the clinician.

Expectedness Definition: The principal investigator ([name]), with input from the co-investigators ([name], [name]) when necessary, will determine whether an adverse event (AE) is expected or unexpected in this population. The principal investigator ([name]) is an expert in non-invasive brain stimulation and will provide his expert opinion in regard to this as well. An AE will be considered unexpected if the nature, severity, or frequency of the event is not consistent with the risk information previously described for the study intervention.

AE and SAE Assessment, Follow-up Procedures:

The occurrence of an adverse event (AE) or serious adverse event (SAE) may come to the attention of study personnel during study visits, or the study participant may report AE or SAEs outside of a scheduled study visit.

All AEs including local and systemic reactions not meeting the criteria for SAEs will be captured on the appropriate case report form (CRF). Information to be collected includes event description, time of onset, clinician's assessment of severity, relationship to study product (assessed only by those with the training and authority to make a diagnosis), and time of resolution/stabilization of the event. All AEs occurring while on study must be documented appropriately regardless of relationship. All AEs will be followed to adequate resolution. Any medical condition that is present at the time that the participant is screened will be considered as baseline and not reported as an AE. However, if the study participant's condition deteriorates at any time during the study, it will be recorded as an AE. Changes in the severity of an AE will be documented to allow an assessment of the duration of the event at each level of severity to be performed. AEs characterized as intermittent require documentation of onset and duration of each episode.

Research personnel will record all reportable events with start dates occurring any time after informed consent is obtained until 7 (for non-serious AEs) or 30 days (for SAEs) after the last day of study participation. At each study visit, research personnel will inquire about the occurrence of AE/SAEs since the last visit. Events will be followed for outcome information until resolution or stabilization. All AEs including local and systemic reactions not meeting the criteria for SAEs will be captured on the appropriate case report form (CRF). Information to be collected includes event description, time of onset, clinician's

assessment of severity, relationship to study product (assessed only by those with the training and authority to make a diagnosis), and time of resolution/stabilization of the event. All AEs occurring while on study must be documented appropriately regardless of relationship. All AEs will be followed to adequate resolution.

Any medical condition that is present at the time that the participant is screened will be considered as baseline and not reported as an AE. However, if the study participant's condition deteriorates at any time during the study, it will be recorded as an AE.

Changes in the severity of an AE will be documented to allow an assessment of the duration of the event at each level of severity to be performed. AEs characterized as intermittent require documentation of onset and duration of each episode.

Research personnel will record all reportable events with start dates occurring any time after informed consent is obtained until 7 (for non-serious AEs) or 30 days (for SAEs) after the last day of study participation. At each study visit, the investigator will inquire about the occurrence of AE/SAEs since the last visit. Events will be followed for outcome information until resolution or stabilization.

Reporting and Documentation Procedures: We will be adopting the following reporting procedures:

What event is reported	When is event reported	By whom is event reported	To whom is event reported
Fatal or life-threatening unexpected, suspected serious adverse reactions	Within 24 hours of initial receipt of information	Investigator	Local/internal IRB
Non-fatal, non-life- threatening unexpected, suspected serious adverse reactions	Within 48 hours of initial receipt of information	Research Personnel	Local/internal IRB
Unanticipated adverse devise effects	Within 7 working days of investigator first learning of effect	Investigator	Local/internal IRB
Unanticipated problem that is not an SAE	Within 7 days of the investigator becoming aware of the problem	Investigator	Local/internal IRB

Participant Notification of New Information: Any new information gained during the study that may affect a participant's willingness to continue in the study will be reported to all currently enrolled participants.

